## Ø Material Used

- American Orthodontics Brackets, Roth prescription, 22 slot size.
- American Orthodontics Elastomeric power chains
- American Orthodontics Elastomeric O-ties
- American Orthodontics Ligature wire.
- Miniscrew, 8 mm length × 1.6 mm diameter TAD (Jeil)
- American Orthodontics Arch wires.
- American Orthodontics Molar bands/tubes.

## D] Outcomes

[figure not shown]
**Primary outcome:** is to monitor the anchorage loss during “En-masse retraction”. All outcomes will be assessed as the difference between T0 at the start of retraction and T1 after complete space closure.

**Secondary outcomes:** is to monitor the changes in the anterior teeth position (final anterior teeth tip, torque and vertical position), rate of space closure, presence of any root resorption and pain associated with the different methods used for retraction.

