## **E] Participant timeline:**

1. The principle investigator will screen the potential patients through careful clinical examination of patients at the Orthodontics and Dentofacial Orthopedics department, Faculty of Oral and Dental Medicine, Future University in Egypt.
2. All recruited patients should fulfill the previously mentioned inclusion and exclusion criteria.
3. Every participant will be asked to sign an informed consent before the beginning of the study.
4. Pre-intervention records will be taken for each participant after enrollment to ensure proper diagnosis.
5. The principle investigator will randomly allocate the patients to one of the intervention groups.
6. Anchorage will be secured by placement of miniscrew, followed by extraction of the first premolar.
7. Active intervention will begin after proper levelling and alignment of teeth through following the wire sequence: 0.014 NiTi, 0.016×0.022 NiTi and 0.017×0.025 StSt.
8. The principle investigator will take pre-retraction records for every participant T0.
9. In Friction mechanics group, Power chain is used for anterior segment retraction while in Frictionless group, T-loop is used for retraction.
10. Each patient will come every 4 weeks for follow up visit, for appliance activation and uptake of impression for interim records.
11. After complete space closure, the principle investigator will take post-retraction records for each participant T1.

- 12.Every patient will fill up a questionnaire regarding his experience during treatment.
- 13.The principle investigator will continue the normal treatment and achieve proper finishing for every patient after the end of the study.

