## **F] Sample size calculation:**

Our sample size calculation is based on a previous study comparing the effect of friction and frictionless mechanics. Using PS software output, we are planning a study of a continuous response variable from independent Group I and Group II subjects with 1 Group I(s) per Group II subject. In a previous study the response within each subject group was normally distributed with standard deviation 0.76. If the true difference in the Group II and Group I means is 1.0, we will need to study 10 Group II subjects and 10 Group I subjects to be able to reject the null hypothesis that the population means of the Group II and Group I are equal with probability (power) 0.8. The Type I error probability associated with this test of this null hypothesis is 0.05. Considering drop out a sample size 15 per group is appropriate.

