**C] Implementation:**

At the time of intervention, the main operator will send the patient to the secretary's office. Then, the assigned employee will open the box and ask the patient to select one envelope. The main operator will assign each participant for the corresponding intervention either (friction or frictionless group) according to the list of codes of randomization.

Assignment to either intervention will occur before levelling and alignment stage.

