**D] Blinding:**

**Blinding of the operators:** Blinding will not be possible for the operators during the application interventions and during the follow up visits. The principal operator is responsible for assigning subjects to interventions according to the concealed allocation, appliance activation at follow up visits, dental impressions and acquisition of dental casts.

**Blinding of the outcome assessors:** It is a single blinded study, therefore, only the outcome assessors will be blind. The patients name will be sealed from pre and post radiographs and study models. Then two assessors will carry out, blindly and Independently, the measurements and analysis of the study.

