## **C] Statistical Analysis:**

- The principle investigator will be responsible for the extraction of the required data from the CBCT taken before and after retraction as well as the study models taken at every follow up visit. The data will be sent to a specialized statistician.
- The specialized statistician will be responsible for the statistical analysis of the study by:
  1. Presenting the data as mean, standard deviation (SD) and Standard error (SE) values.
  2. Using Paired t-test to compare between the friction and the frictionless group of retraction as well as to compare between the pre-and post -treatment data for each group.
  3. Using Anova test to determine the rate of anterior segment retraction.
  4. Statistically evaluate the patient acceptance for both techniques.
- For this study, the specialized statistician will use IBM11 SPSS12 Statistics Version 20 for Windows to perform the required statistics.
- The significance level will be  $P \leq 0.05$ . Highly significant variables are detected when P value is less than 0.01.

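### Arms are compared on unadjusted T1-T0 change, by a paired test on independent groups; a model adjusting for T0 would be a cheap improvement for the continuous outcomes

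*Protocol*

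**What the plan says.** Protocol, D] Outcomes: "All outcomes will be assessed as the difference between T0 at the start of retraction and T1 after complete space closure".

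C] Statistical Analysis gives the between-arm method as "Using Paired t-test to compare between the friction and the frictionless group of retraction". The same item uses the paired test for pre/post comparison within each group. Retraction rate has its own line: "Using Anova test to determine the rate of anterior segment retraction". No covariate is named anywhere.

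E] Participant timeline: "The principle investigator will take pre-retraction records for every participant T0". A] Data collection methods has anchorage loss, torque, tip, vertical position and molar rotation each measured before and after retraction, on CBCT or digital models.

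Study design describes two parallel arms allocated 1:1, and F] Sample size calculation treats them as independent groups. A] Sequence generation is a simple spreadsheet random sort without stratification. On timing, C] Implementation says: "Assignment to either intervention will occur before levelling and alignment stage". T0 records follow that stage.

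**The concern.** Two choices are fixed here, and neither serves the design well.

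First, a paired test needs pairs. Nothing in the protocol matches a friction patient to a frictionless patient, so the named between-arm test contradicts the parallel-group design and the sample size calculation.

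Second, even with the test corrected to its independent-samples form, the comparison ignores the T0 value already held for each patient. With 10 to 15 per arm and unstratified allocation, T0 means can differ noticeably by chance. Eligibility admits both bimaxillary protrusion and Class II division 1 cases, so varied starting positions are plausible. Whenever T0 and T1 are imperfectly correlated, an unadjusted change carries part of that imbalance into the estimate. At stake are some precision and protection against an unlucky allocation, not the validity of the trial.

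**Working it through.** **Inputs.** From F] Sample size calculation: difference 1.0, SD 0.76, 10 evaluable and 15 enrolled per arm. Alpha: "The Type I error probability associated with this test of this null hypothesis is 0.05". Power: the null hypothesis is that the means "are equal with probability (power) 0.8". Assumed, because the protocol does not say: a two-sided test, 0.76 as the SD of change, equal T0 and T1 variances, and r, which is shown as a range.

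**1. The plan's own figure.** n per arm = 2 × [0.76 × (1.960 + 0.842) / 1.0]² = 9.07, rounded up to 10. The stated figure reproduces as a two-sided, independent-groups calculation; a one-sided alpha would give 8. Noncentral-t power for the unadjusted change comparison is 0.795 at 10 per arm and 0.935 at 15.

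**2. Paired versus independent.** Ten arbitrary pairs leave 10 − 1 = 9 degrees of freedom. Two independent groups of 10 leave 20 − 2 = 18, which is the structure the sample size assumes.

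**3. Effect of chance imbalance.** The SD of the T0 difference between arms is √(2/15) = 0.365 T0 SDs at 15 per arm and √(2/10) = 0.447 at 10. The change score carries (1 − r) of it. The T0 SD implied by a change SD of 0.76 is 0.76/√(2(1 − r)).

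- r = 0.5, 15 per arm: 0.5 × 0.365 × 0.76 = 0.14, against a planned difference of 1.0.
- r = 0.5, 10 per arm: 0.5 × 0.447 × 0.76 = 0.17.
- r = 0.9, 15 per arm: 0.1 × 0.365 × 1.70 = 0.06.

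**4. Precision.** In large samples, the variance of the T0-adjusted comparison divided by that of the change score is (1 − r²)/[2(1 − r)] = (1 + r)/2. Estimating the slope multiplies this by (N − 3)/(N − 4), with N the total evaluable: 17/16 = 1.063 at 10 per arm and 27/26 = 1.038 at 15. The power columns come from 40,000 simulated trials per setting, with the change SD held at 0.76.

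| r | (1+r)/2 | Net ratio, 10/arm | Adjusted power, 10/arm | Net ratio, 15/arm | Adjusted power, 15/arm |
|---|---|---|---|---|---|
| 0.3 | 0.65 | 0.691 | 0.916 | 0.675 | 0.988 |
| 0.5 | 0.75 | 0.797 | 0.874 | 0.779 | 0.976 |
| 0.7 | 0.85 | 0.903 | 0.833 | 0.883 | 0.958 |
| 0.9 | 0.95 | 1.009 | 0.788 | 0.987 | 0.937 |
| 0.95 | 0.975 | 1.036 | 0.780 | 1.012 | 0.933 |
| 0.98 | 0.99 | 1.052 | 0.772 | 1.028 | 0.928 |
| Unadjusted change | | 1 | 0.795 | 1 | 0.935 |

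**5. Break-even.** Setting the net ratio to 1 gives r = 2 × 16/17 − 1 = 0.88 at 10 per arm and r = 2 × 26/27 − 1 = 0.93 at 15.

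**The case against.** The strongest case against is that nothing needs repair beyond the word paired. Anchorage loss is a displacement, so change is its natural measure. Under randomisation, the difference in mean change is unbiased. Covariate adjustment is commonly left to the SAP, which is not at hand. No r is given, and a high one is plausible for tooth positions read against fixed reference planes, where the gain disappears. If all 15 per arm are evaluable, unadjusted power is already about 0.935.

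Most of that stands and limits the point. It does not remove it: the protocol does not leave the method open, but defines the outcomes as change and names a test without covariates. A model of change on arm and T0 keeps change as the measure and gives the same arm effect as a model of T1.

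A second objection is that T0 is not a pre-randomisation baseline. Assignment precedes levelling and alignment, and for the operators "Blinding will not be possible for the operators during the application interventions and during the follow up visits". Adjustment therefore assumes that the arms are treated alike until T0. The described steps up to T0 (bonding, miniscrews, extraction, wire sequence) are common to both arms, and the mechanics diverge only when retraction begins. The change score relies on the same T0, so its timing gives no reason to prefer the unadjusted analysis.

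A reader might infer more: that the change score is biased, that adjustment always gains precision and costs nothing, or that it suits every outcome. None of these is supported. The bias is conditional on a realised imbalance, the gain vanishes at high r in a trial this small, and several outcomes are unsuitable for a linear T0 adjustment. Root resorption is a five-grade score and retraction rate has its own ANOVA. Pain has a questionnaire handed out before retraction, but it is not clear that a T0 score is recorded.

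**Conclusion.** A cheap improvement, limited to the continuous CBCT and digital-model outcomes, together with one contradiction to correct: the paired between-arm test.

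At 10 evaluable per arm, adjusting for T0 cuts the variance by about 20% at r = 0.5 and 10% at r = 0.7, and changes it by about +1% at r = 0.9. In power, that is a gain of about 8 points at r = 0.5 against a worst loss of about 2 points in the range examined (r up to 0.98). At 15 per arm both the gain and the loss in power are smaller. These sizes rest on the assumed r, equal T0 and T1 variances, and 0.76 being the SD of change. The protection against chance T0 imbalance does not depend on r being low, although the imbalance matters less as r rises.

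**What to change.** In C] Statistical Analysis:

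- Replace the between-arm paired t-test with a prespecified linear model of T1 (or T1-T0) on arm and that outcome's T0 value. Apply it to linear and angular anchorage loss, torque, tip, vertical position and molar rotation. Report the adjusted difference with its 95% CI.
- Name an independent-samples t-test on change as the sensitivity analysis. Keep the paired test only for within-arm description.
- State that both arms are managed identically from assignment until T0.
- Leave root resorption grade and retraction rate out of this model. Include pain only if a T0 score is actually recorded.

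Keep 15 per arm: without a documented r, there is no basis for a reduction.

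The cost is a few lines of text, one residual degree of freedom and the small loss at very high r shown above. No new visit, scan or patient is needed. Fixing the model now also prevents a choice between adjusted and unadjusted results after the data are seen.

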## **E] Participant timeline:**

1. The principle investigator will screen the potential patients through careful clinical examination of patients at the Orthodontics and Dentofacial Orthopedics department, Faculty of Oral and Dental Medicine, Future University in Egypt.
2. All recruited patients should fulfill the previously mentioned inclusion and exclusion criteria.
3. Every participant will be asked to sign an informed consent before the beginning of the study.
4. Pre-intervention records will be taken for each participant after enrollment to ensure proper diagnosis.
5. The principle investigator will randomly allocate the patients to one of the intervention groups.
6. Anchorage will be secured by placement of miniscrew, followed by extraction of the first premolar.
7. Active intervention will begin after proper levelling and alignment of teeth through following the wire sequence: 0.014 NiTi, 0.016×0.022 NiTi and 0.017×0.025 StSt.
8. The principle investigator will take pre-retraction records for every participant T0.
9. In Friction mechanics group, Power chain is used for anterior segment retraction while in Frictionless group, T-loop is used for retraction.
10. Each patient will come every 4 weeks for follow up visit, for appliance activation and uptake of impression for interim records.
11. After complete space closure, the principle investigator will take post-retraction records for each participant T1.

- 12.Every patient will fill up a questionnaire regarding his experience during treatment.
- 13.The principle investigator will continue the normal treatment and achieve proper finishing for every patient after the end of the study.

## **F] Sample size calculation:**

Our sample size calculation is based on a previous study comparing the effect of friction and frictionless mechanics. Using PS software output, we are planning a study of a continuous response variable from independent Group I and Group II subjects with 1 Group I(s) per Group II subject. In a previous study the response within each subject group was normally distributed with standard deviation 0.76. If the true difference in the Group II and Group I means is 1.0, we will need to study 10 Group II subjects and 10 Group I subjects to be able to reject the null hypothesis that the population means of the Group II and Group I are equal with probability (power) 0.8. The Type I error probability associated with this test of this null hypothesis is 0.05. Considering drop out a sample size 15 per group is appropriate.

## **G] Recruitment strategy:**

The principal investigator will recruit the patients from the clinic of Orthodontics and Dentofacial Orthopedics department, Faculty of Oral and Dental Medicine - Future University in Egypt.

Screening of patients will continue until the total number of participants for the study is collected.

## **II) Assignment of interventions:**

### **A] Sequence generation:**

The supervisor of the study will apply Computer generated random numbers to randomly assign patients to group A (Frictionless) or B (friction) using Microsoft Office Excel 2007 sheet. The patient numbers will be written in the first column, and the supervisor will select function RAND()to generate the randomization number in the second column. These numbers will be sorted according to the randomization number so the first column numbers will be randomly distributed.

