## **Study design:**

This is a randomized clinical trial with two arms parallel group, and 1:1 allocation ratio. In one group, frictionless mechanics will be applied during “En-masse retraction” while the other will receive frictional mechanics during retraction. The anchorage loss will then be compared between both interventions.

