#### **B] Eligibility criteria:**

➢ **Inclusion criteria:**for the participants include the following:

1. Orthodontic patients (both genders)
2. Age range (14-24)
3. Patients requiring 1st premolars extraction followed by “En-masse retraction” (Bimaxillary Protrusion or Class II division 1 cases).
4. Patients with fully erupted permanent teeth (not necessarily including the 3rd molar).
5. Cases requiring maximum anchorage during anterior segment retraction.
6. Cases with minimal crowding (2-3) mm

➤ **Exclusion Criteria:** for the involved subjects included:

1. Patients suffering from any systemic diseases interfering with tooth movement.
2. Patients with extracted or missing permanent teeth. (except for third molars).
3. Patients with badly decayed teeth.
4. Patients with any parafunctional habits (i.e. Bruxism, tongue thrusting, mouth breathing, etc....).
5. Patients with previous orthodontic treatment

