***Friction group:***

- Crimpable hooks added to the arch wire (0.017"x0.025" Stainless steel) distal to the lateral incisor passing near the center of resistance of the anterior segment.
- A ligature wire extending between the second premolar and miniscrews will be used for proper anchorage control.
- Retraction will start on a 0.017"x0.025" Stainless steel wire using elastomeric chain (force applied will be 200 g per side) [43] extending between the crimpable hooks and the miniscrews.
- The force will be measured by a force gauge and reactivated every 4 weeks maintaining constant force of retraction all over the retraction phase.

➢ **Follow up visits**

Patients will be asked to attend for follow up sessions every 4 weeks for:

- Evaluation miniscrews stability.
- Replacement of the power chain to maintain a force of 200 gm per side.
- Reactivation of the T-loop by further distal activation and cinch back.
- Impression taking to determine the anchorage loss

➤ **Criteria for discontinuing or modifying the allocated intervention:**

In cases of prolonged swelling or pain related to the miniscrews, the patient will be given strict oral hygiene measures and may wait for three weeks before the beginning of retraction.

In cases of loose or broken miniscrews, the screw will be removed and replace the miniscrew after total resolution of the inflammation.

➤ **Criteria for Ending the retraction:**

a-class I canines

b-normal overjet

c- closure of extraction space

d- reaching good profile

Ø **Post-retraction Questionnaire:**

The patients of both groups will be asked to fill in questionnaires regarding their experience with their allocated technique during the whole retraction period from day of extraction till the end of retraction.

Ø **Retraction records**

Following “En-masse retraction”, patients will be referred to the same radiology center to acquire the final cone-beam CT to assess the movement and inclination of anterior teeth.

The final dental model will be used to assess the rate of retraction and molar anchorage loss achieved throughout the study.

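### Malocclusion type, known at eligibility and plausibly prognostic, is left out of the named between-arm test; with about 30 patients on one unstratified list this costs precision and conditional validity

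*Protocol*

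**What the plan says.** All references are to the protocol.

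- **Eligibility criteria** (inclusion 3) admits two diagnoses: "Bimaxillary Protrusion or Class II division 1 cases". Inclusion 5 narrows the sample: "Cases requiring maximum anchorage during anterior segment retraction". Crowding must also be minimal. The expected mix of the two types is not given.
- **Study design**: "This is a randomized clinical trial with two arms parallel group, and 1:1 allocation ratio".
- **Sequence generation** describes one spreadsheet list ordered by a random number: "These numbers will be sorted according to the randomization number so the first column numbers will be randomly distributed". No strata or blocks are named. **Implementation** has each patient pick an envelope from a box, before levelling and alignment.
- **Criteria for ending the retraction** (under Interventions) lists four items. Two are occlusal relations, "a-class I canines" and "b-normal overjet"; a third is closure of the extraction space. **Outcomes** defines every outcome as a change from the start of retraction to complete space closure.
- **Sample size calculation** assumes outcomes "normally distributed with standard deviation 0.76" and a target expressed as "If the true difference in the Group II and Group I means is 1.0", with 80% power and alpha 0.05. It arrives at 10 per group, raised to 15 for drop-out.
- **Statistical Analysis** names a paired t-test between the arms and an ANOVA for the rate of retraction. Neither is given a baseline factor.

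**The concern.** Part of the stopping rule is a fixed occlusal target, so the movement a patient needs depends on where that patient starts. Class II division 1 and bimaxillary protrusion plausibly start at different distances from Class I canines and normal overjet. If so, type predicts both anchorage loss and the rate of closure. Measuring change from the start of retraction does not remove this, because the change itself is what depends on the distance.

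Simple allocation of about 30 patients can leave the types unevenly split between arms. An analysis that ignores type then carries that imbalance into the estimated difference, and leaves between-type variation in the error term even when the split is even. The trial is randomised once, so what matters to its reader is the error rate given the split that actually occurred, as well as the average over all possible splits.

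**Working it through.** **Inputs from the protocol.** SD 0.76, target difference 1.0 (unit not stated, read as mm), power 0.80, alpha 0.05 (taken as two-sided), 10 per group raised to 15. The total of 30 follows from 2 × 15; Sequence generation gives no list length.

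**Assumptions.** Equal arms; half the patients of each type; a mean difference D in anchorage loss between types of 0.25 to 1.0 mm. Neither the mix nor D is in the protocol.

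**1. The plan's own figure.** n = 2 × (1.960 + 0.842)² × 0.76² / 1.0² = 9.07, rounded up to 10. This reproduces the stated size. Exact two-sample t power is 0.795 at 10 per group and 0.935 at 15.

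**2. How often the types split unevenly.** With 15 of each type and 15 per arm, the number of one type in one arm is hypergeometric (30, 15, 15).

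| Split of one type between arms | Probability |
|---|---|
| 8 v 7 (best possible) | 0.534 |
| 9 v 6 or worse | 0.466 |
| 10 v 5 or worse | 0.143 |
| 11 v 4 or worse | 0.027 |

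The imbalance in shares has SD 0.186. It falls to 0.17 for a 30:70 mix and 0.15 for 20:80. With 10 completers per arm and a 50:50 mix, 7 v 3 or worse has probability 0.179.

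**3. Shift in the between-arm difference.** Shift = D × (difference between arms in the share of one type). For 10 v 5 that share is 5/15 = 0.333.

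| D (assumed) | Shift at 10 v 5 | SD of shift over all allocations (0.186 × D) |
|---|---|---|
| 0.25 mm | 0.08 mm | 0.05 mm |
| 0.5 mm | 0.17 mm | 0.09 mm |
| 1.0 mm | 0.33 mm | 0.19 mm |

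For scale, the standard error of the comparison at 15 per arm is 0.76 × √(2/15) = 0.28 mm. With 10 completers per arm, a 7 v 3 split shifts the difference by 0.4 × D, which is 0.20 mm at D = 0.5 and 0.40 mm at D = 1.0.

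**4. Error rate.** In 100,000 simulated allocations per value of D (within-type SD 0.76, 15 per arm), an unadjusted two-sample t-test rejects a true null in 5.0% of trials at D = 0.5 and 4.9% at D = 1.0. Among allocations split 10 v 5 or worse, it rejects in 8.3% and 15% respectively.

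**5. What adjustment returns.** If 0.76 is the SD of a 50:50 mix, the residual SD after adjustment is √(0.76² − D²/4).

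| D | Residual SD | Power at 10 per arm (18 df) |
|---|---|---|
| 0 | 0.76 | 0.795 |
| 0.25 | 0.75 | 0.81 |
| 0.5 | 0.72 | 0.84 |
| 1.0 | 0.57 | 0.96 |

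Spending one degree of freedom on the factor (17 df) lowers 0.795 to 0.792 when type is irrelevant, before the small variance cost of any chance imbalance.

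If instead 0.76 came from a single-type sample, the SD in a 50:50 mix is √(0.76² + D²/4), which is 0.80 at D = 0.5 and 0.91 at D = 1.0. Unadjusted power at 10 per group is then 0.75 or 0.64, and at 15 per group 0.91 or 0.83.

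**The case against.** The strongest reply is that nothing here is invalid. Simple randomisation of 30 patients is legitimate, chance imbalance is not bias, and the unconditional type I error stays near 0.05. If 0.76 describes a similar mix, the variation between types is already in the sample size. All of that stands, and it is why the point concerns precision and conditional validity only.

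Second, the link to outcome is inferred. The protocol gives no starting canine relation or overjet by type and never says that type affects anchorage loss. Every patient also runs to space closure, needs maximum anchorage and has miniscrews, whichever the arm. This stands too: it may make the gap small, though it does not show that the gap is zero.

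Third, covariates are often left to an analysis plan, which may exist here. That weakens any complaint of omission. However, the protocol does name a between-arm test, and that test has no place for type.

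A reader might infer that imbalance could shift the result by a large share of the 1.0 target, say 0.5 mm. The documents do not support that. A 10 v 5 split gives 0.50 mm only if D = 1.5 mm. Type would then explain 1.5²/4 ÷ 0.76² = 97% of the variance behind the stated SD and leave a residual SD of 0.12. At D = 1.0 mm, a shift of 0.5 mm or more has probability 0.3%.

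**Conclusion.** The point holds as a moderate design weakness. Two malocclusions share one unstratified list, and the named between-arm test ignores a factor that is known at eligibility and plausibly prognostic. Under a 50:50 mix and 15 per arm, about one allocation in seven splits 10 v 5 or worse. A 10 v 5 split moves the difference by about 0.1 to 0.3 mm for assumed gaps of 0.25 to 1.0 mm. A less even mix makes imbalance smaller; fewer completers make it larger. The size rests wholly on an assumed gap. The case for acting is that adjustment costs almost nothing if the gap is nil and gains power if it is not: at 10 per arm, 0.795 becomes 0.792 in the first case and about 0.84 at a gap of 0.5 mm. The planned sample size does not need to change.

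**What to change.** In Statistical Analysis, state that the arms will be compared on anchorage loss and on retraction rate with a linear model for independent groups, with treatment arm and malocclusion type (two levels, as recorded at eligibility) as prespecified fixed factors. This also takes the place of the paired test now named between the arms, which does not suit two separate groups of patients. The cost is one degree of freedom and a negligible power loss if type is not prognostic. No patients, visits or measurements are added, and the change can still be made after patients have been randomised, provided it is fixed before the outcomes are compared.

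Stratified allocation is optional. Separate blocked lists per type would do nothing under the present Implementation section, because a free draw from a box destroys the block order. If stratification is chosen, that section must also change to opening envelopes in sequence within each stratum. Block sizes should not be disclosed to the operator, who is unblinded under Blinding and could otherwise anticipate assignments. With about 30 patients and unknown stratum sizes, the extra balance may not justify that handling once the model includes type.
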